#### **14.6 Criteria for discontinuation**

A participant must be discontinued in the IMP treatment if any of the following is present:

- Female patients in the intervention study who become pregnant, intend to become pregnant or do not use adequate birth control (according to inclusion criteria 7, in section 7.1).
- Experience of research-related injury or unacceptable side effects to the study medication.
- Safety considerations assessed by the investigator
- Treatment with Lithium (ATC: N05AN).
- Treatment with potassium sparing diuretics (ATC: C03D, C03E).
- Confirmed eGFR below 15 ml/min/1.73 m^2.
- Confirmed elevated liver enzyme (ASAT and/or ALT) 3 times above normal range.

Discontinued patients will be offered tests corresponding to the final study visit. Data on all patients will be included in the study and will be used in safety analysis.

After discontinuation of study medication in the randomized population, observation should continue with visits as planned in the observational group (if the patient accepts), or if that is not possible/acceptable, evaluation of vital status and development of endpoints should be evaluated through registries, information of hospitals and GPs, or interviews with the patient as appropriate and possible in order to monitor development of endpoints in all included patients as thoroughly as possible, provided that the patient agrees.

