	
The expected relative proportions of diabetes type 2 patients developing microalbuminuria in our study population are: 24% in patients at high-risk for diabetic nephropathy in the treatment group, 40% in those patients at high-risk for diabetic nephropathy in the placebo group and 8.5% in those therapy-naive patients at low-risk for diabetic nephropathy. Using the samples size formula for two proportions test (<math>\alpha=0.05</math> <math>\beta=0.80</math>), randomized (1:1), <math>n=129</math> in each arm of the intervention group. To account for drop-outs we plan to randomize 300 in all. It is expected that approx. 15% of the population will show a pattern of high-risk of CKD, therefore 2000 patients have to be included. Equal drop-out frequency is expected in both groups and there will be no replacement of drop-out. Discontinuation prior randomization is categorized screening failure.
 
Analysis populations: The primary analysis will be conducted for all patients included (intent-to-treat population) in the observational and intervention study groups. In addition, all relevant efficacy endpoints will be also analyzed for the per protocol population in both study groups.
 
Analysis of primary endpoint: Cox regression analysis of development of the primary endpoint adjusted for age, gender, study site will be conducted in both study groups (observational and intervention) and for study intervention in the interventional group. Secondly adjusted in addition for baseline UACR, HbA1c and BP.
 
Analysis of secondary endpoints: Cox regression analysis of development of secondary endpoints in the both study groups (observational and intervention) as well within the interventional group (high- vs. low-risk), adjusted for age, gender, study site and study intervention with secondary adjustment for baseline UACR, HbA1c and BP.
 
Assessment of safety: The assessment of safety will be based primarily on the frequency of eCRF-documented AEs, laboratory abnormalities, and SAEs (see section 13.3). Occurrence and frequency of eCRF-documented AEs, SAEs and laboratory abnormalities will be summarized by treatment group.
 
In addition AEs leading to death and AEs leading to discontinuation of study medication and/or withdrawal will be summarized for the two treatment groups.
 
Final analysis plan: Statistical analysis of the data will be performed by Steno Diabetes Center. A statistical analysis plan will be written and signed before database lock and unblinding of the entire treatment code.
 
Methods for imputation and type of censoring will be clarified in the statistical analysis plan prior to database lock and unblinding.

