## 6.2 Observation group (group A) / Low-risk population

It is expected that 85% of the total population (approx. 1700 patients) will show a low-risk pattern. Patients should be followed by the investigator in routine clinics or seen once yearly, for standard diabetes care according to local guidelines. Annual measurements of UACR, BP, medication, and locally measured creatinine, sodium, potassium, and lipids (cholesterol, HDL, LDL, triglycerides) will be performed. HbA1c will be measured in DCCT-aligned quality control programs or IFCC. During the study, the medical history regarding vascular events, current retinopathy status (by history) and information on laser treatment, as well significant medical events (see section 10.14.), including hospital admissions, are registered.

Secondary endpoints and significant medical events will be registered at the annual visits.

After the last study visit, patients will continue in the observational long-term follow-up in accordance with section 6.4.

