## 6.3 Intervention group (group B) / High-risk population

Randomized, double-blind, placebo-controlled, multicenter study in the high-risk population based on urinary proteomic risk pattern assessment. It is estimated that 15% of the total population (approx. 300 patients) will show a high-risk pattern.

Patients will be invited to participate if the urinary proteomic pattern after the screening visit is showing a high-risk pattern, and if at least two of the three samples from the "run-in"-period show normoalbuminuria (UACR <30 mg/g) analyzed at the central laboratory.

Patients in the intervention study will be randomized (1:1) to spironolactone 25 mg daily or matching placebo in addition to standard treatment according to the investigators discretion. Patients will be stratified in the two treatment arms (1:1) based on whether or not the patients is treated with RAS blocking agents at the time of entry (Screening).

Patients are seen according to Table 1, with a study visit every 13th weeks. Patients must be treated by the investigator for standard diabetes care according to local guidelines. Dependent on time of baseline the patients will be treated for at least 104 weeks with measurements of UACR, BP, medication, and locally measured creatinine, sodium, potassium, and lipids (cholesterol, HDL, LDL, triglycerides). HbA1c will be measured in DCCT-aligned quality control programs or IFCC. At screening and in the duration of the study, the medical history regarding vascular events, current retinopathy status (by history) and information on laser treatment, as well as adverse events (see section 13.3), including hospital admissions, are registered.

Potassium levels will be measured locally as indicated in table 1.

Secondary endpoints and adverse events (see section 13.3) will be registered at the visits every 13 weeks.

After the last study visit patients will continue in the observational long-term follow-up in accordance with section 6.4.

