### 11.3 Main side effects of spironolactone

Gynecomastia may develop in association with the use of spironolactone. Development appears to be related to both dosage level and duration of therapy and is normally reversible when the drug is discontinued. In rare instances some breast enlargement may persist.

The following adverse events have been reported in association with spironolactone therapy:

Organ system	Side effect
General disorders and administration site conditions	malaise
Neoplasms benign, malignant and unspecified (including cysts and polyps)	benign breast neoplasm
Gastrointestinal disorders	gastrointestinal disturbances, nausea
Blood and lymphatic system disorders	leukopenia (including agranulocytosis), thrombocytopenia
Hepatobiliary disorders	hepatic function abnormal
Metabolism and nutrition disorders	electrolyte disturbances, hyperkalemia
Musculoskeletal disorders	leg cramps
Nervous system disorders	dizziness
Psychiatric disorders	changes in libido, confusion
Reproductive system and breast disorders	menstrual disorders, breast pain
Skin and subcutaneous tissue disorders	Stevens-Johnson syndrome (SJS), toxic epidermal necrolysis (TEN), drug rash with eosinophilia and systemic symptoms (DRESS), alopecia, hypertrichosis, pruritus, rash, urticaria
Renal and urinary disorders	acute renal failure

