### **24.5 Continuation of study medication**

If the potassium level is  $< 0.9$  mmol/L above upper reference range the patient can continue taking study medication.

Patients who continue study medication after temporary discontinuation of study medication must have the potassium measured according to section 24.2.5

In a patient who has experienced a potassium level of  $\geq 1.4$  mmol/L above upper reference range, and in whom the potassium fails to decrease to  $< 0.9$  mmol/L above upper reference range after the procedures described above have been tried, the study medication must be discontinued permanently and it should be recorded in the eCRF.

In case of repeated episodes of confirmed hyperkalemia after the attempt to re-start study medication following discontinuation the study medication must be discontinued permanently and it should be recorded in the eCRF.

Patients, who discontinue the study medication, will remain in the study and be followed for the full duration of the study.

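### Randomised patients who stop study drug without withdrawing, and have no further central UACR, are counted event-free to study end; if stopping differs by arm, this biases the active-versus-placebo hazard ratio

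*Protocol*

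**What the plan says.** **On drug.** Protocol 6.3: "Patients are seen according to Table 1, with a study visit every 13th weeks". SAP 6.3.1.3 confirms that the high-risk stratum has the primary outcome measured about every three months.

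**After stopping drug.** Protocol 14.6 gives three routes:
- An exit examination: "Discontinued patients will be offered tests corresponding to the final study visit".
- Continued observation on the low-risk group's plan: "After discontinuation of study medication in the randomized population, observation should continue with visits as planned in the observational group (if the patient accepts"). Under Protocol 6.2 that plan means "Annual measurements of UACR, BP, medication, and locally measured creatinine, sodium, potassium, and lipids".
- Where visits are not possible or acceptable, "evaluation of vital status and development of endpoints should be evaluated through registries, information of hospitals and GPs, or interviews with the patient". None of these sources assures three first-morning voids analysed centrally.

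Protocol 24.5 adds, after hyperkalaemia, "Patients, who discontinue the study medication, will remain in the study and be followed for the full duration of the study".

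**Analysis.** Protocol 15.6 defines the endpoint as time to the first qualifying UACR set. Protocol 15.5 leaves the type of censoring to the SAP. SAP 5.4 measures follow-up from baseline to end and uses the last observation only for participants who withdraw. SAP 6.2 states that no method for missing data and no censoring will be used. SAP 6.3.2.1 compares active with placebo by Cox regression in the intention-to-treat cohort. The only sensitivity analysis for that comparison (6.3.2.3) is a subgroup forest plot. Unequal UACR frequency is addressed only for high versus low risk (6.3.1.3 and 6.4).

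**The concern.** The endpoint can be detected only in a central three-void set. Two things follow for a patient who stops drug.

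- **Exposure.** With no further central set, the patient cannot have an event, yet the SAP as written keeps the patient in the risk set to study end. That is event-free time in which nobody looked.
- **Looks.** With annual sets, the patient has fewer chances of a first positive than a patient on 13-week sets. This matters only if positives do not persist, since a persistent one is found at the next annual set, merely later.

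Both cancel if the arms stop drug equally. If more stop on spironolactone, the hazard ratio falls below 1 with no drug effect; if more stop on placebo, it rises. Spironolactone's known side effects ("Gynecomastia may develop in association with the use of spironolactone", and hyperkalaemia) make an imbalance plausible, not certain. At stake is the estimate for the SAP's second hypothesis.

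**Working it through.** **1. The plan's own figures.** With 40% versus 24%, two-sided 0.05 and 80% power, the unpooled formula gives (1.960 + 0.842)² × (0.40×0.60 + 0.24×0.76) / 0.16² = 129.5, matching the stated 129 per arm. The planned hazard ratio is ln(0.76)/ln(0.60) = 0.537. With no drug effect and 40% risk in both arms of 150, 120 events are expected, so the standard error (SE) of the log hazard ratio is about 2/√120 = 0.18. Simulation gave 0.18–0.19.

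**2. Assumptions.** The documents give no stopping rates, no share of stoppers without UACR and no UACR variability. Assumed:
- active/placebo stopping of 20/10% or 30/10%, spread over follow-up or all in year 1;
- 30% of stoppers without later central UACR;
- follow-up uniform over 104–230 weeks (mean 167);
- an exit test taken by 80% of stoppers.

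**3. Unequal looks alone.** Null hazard ratio by simulation, with 40% risk under 13-week looks:

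| Active/placebo stopping | Persistent endpoint | UACR trajectories with measurement noise (two settings) | Fully transient (bound) |
|---|---|---|---|
| 20/10%, spread | 0.998 | 0.987, 0.983 | 0.968 |
| 30/10%, spread | 0.995 | 0.974, 0.967 | 0.937 |
| 30/10%, year 1 | 0.991 | 0.951, 0.935 | 0.880 |
| 10/20%, spread | 1.002 | 1.013, 1.017 | 1.032 |

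A separate simulation with different noise assumptions gave 0.987 and 0.978 (20/10%, spread) and 0.974 and 0.966 (30/10%, spread), and 0.99–1.01 with equal 10/10% stopping. UACR sets per patient-year hardly differ: 3.9 versus 4.0 (20/10%) and 3.8 versus 4.0 (30/10%). At 150 per arm with spread stops, two-sided type I error was 4.6–5.4% (20/10%) and 5.1–5.9% (30/10%).

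**4. Adding unobserved event-free time.** A rough check: the share of follow-up with no look is 30% × stopping rate × fraction of follow-up after the stop. That fraction is about 1/2 for spread stops and (167 − 26)/167 = 0.84 for year-1 stops. The added factor is the ratio of observed shares.
- 20/10%, spread: (1 − 0.030)/(1 − 0.015) = 0.985
- 30/10%, spread: (1 − 0.045)/(1 − 0.015) = 0.970
- 30/10%, year 1: (1 − 0.076)/(1 − 0.025) = 0.948

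The look effect still applies to the other 70% of stoppers, so multiply by the step 3 value raised to the power 0.7. For the persistent and fully transient models:
- 20/10%, spread: 0.985 × 0.998^0.7 = 0.983 and 0.985 × 0.968^0.7 = 0.963
- 30/10%, spread: 0.970 × 0.995^0.7 = 0.966 and 0.970 × 0.937^0.7 = 0.926

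Full simulation over the four models gave 0.962–0.981 and 0.925–0.964, in close agreement. Leaving out the fully transient bound, the range is about 0.94–0.98. For 30/10% in year 1 the trajectory models give 0.948 × 0.951^0.7 = 0.915 and 0.948 × 0.935^0.7 = 0.904; simulation gave about 0.90.

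**5. Size against precision.** |ln 0.94| = 0.062 is about a third of an SE; |ln 0.98| = 0.020 is about a tenth.

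**6. Effect of each remedy.** Ending exposure at the last central set removes the shift added in step 4 and leaves the step 3 values. Using annual and end-of-study sets only, with exposure ended in the same way, gave 0.998–1.000 when detection does not change later treatment. But Protocol 12.4 flags the endpoint to the investigator and asks that patients not on ACE inhibitors or ARBs start none before it. If 60% of detected patients then start treatment and UACR falls by 30% (both assumed), the annual-only null hazard ratio is about 1.01–1.04, with 20–25% of placebo patients having an event.

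**The case against.** **The trigger is unproven.** No document reports stopping by arm, and the synopsis says "Equal drop-out frequency is expected in both groups and there will be no replacement of drop-out". This stands as a limit on the claim, although drop-out from the study is not the same as stopping drug.

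**The effect is small.** This stands. With spread stops, looks alone leave type I error near nominal. The two-of-three-void rule with its geometric-mean condition should limit transient positives, so the fully transient model is a bound.

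**The SAP already ends exposure at the last observation.** Only for those who withdraw. Protocol 14.5 does speak of withdrawal from study treatment, so a lenient reading could include drug-stoppers. The no-censoring statement may also mean only that no data are discarded, since SAP 6.4 uses the term for restricting to annual samples. Even then, nothing says that the last observation must be a central UACR set rather than a registry or telephone contact.

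**Other planned analyses help.** The UACR mixed model depends far less on the number of looks, and the per-protocol cohort mostly stays on 13-week visits. Neither gives a look-balanced intention-to-treat estimate of the primary endpoint.

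**Stronger readings to resist.** A reader might infer that the design favours spironolactone. The documents do not support that: the direction depends on unknown stopping rates. A reader might take an annual-only model as the unbiased answer; step 6 shows that it need not be. A reader might see a contradiction between Protocol 14.6, 24.5 and Table 1. There is none: they give the schedule after stopping, the duration of follow-up and the visit weeks.

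**Conclusion.** The point holds as a conditional, low-priority one. The firm part is textual: for the primary endpoint, the SAP does not end event-free time when central UACR ends, and read literally it runs that time to study end. The numerical part rests on assumed stopping rates and on 30% of stoppers lacking UACR. On those assumptions the null hazard ratio is about 0.94–0.98 with spread stops and about 0.90 with 30/10% stopping all in year 1. Unequal looks account for about 0.96–0.99 of the spread-stop figure, vanish with equal stopping and nearly vanish if microalbuminuria persists. All of this is small beside the SE of 0.18–0.19 and the planned hazard ratio of 0.537. It could matter for a borderline result, and it is cheap to settle before unblinding.

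**What to change.** 1. **SAP 5.4 and 6.2.** State that, for the primary endpoint, exposure without an event ends at the last central three-void UACR set, in place of the no-censoring statement. This costs one sentence and one assumption to declare: that losing central UACR is unrelated to later UACR.

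2. **Reporting by arm.** Tabulate the number and timing of permanent study-drug stops, UACR sets per patient-year, and the number of patients without central UACR follow-up. The data already exist. If stopping is balanced, the table settles the matter.

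3. **Optional, SAP 6.3.2.3.** Add a supportive intention-to-treat Cox model of active versus placebo using only scheduled annual and end-of-study sets in both arms, without exit tests. The carry-forward of 6.3.1.3 is no substitute: it keeps the extra detections and moved the null hazard ratio by only about 0.01. Disclose two limits. Power falls: in the two trajectory models to 78% and 70%, against 82–89% with all sets across the four models, and further if treatment starts after a flagged endpoint. And the model is not unbiased by construction (step 6). Read it beside the main result, not as a correction of it.

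No change to visits or treatment is requested.

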## 15 STATISTICAL CONSIDERATIONS

### 15.1 Sample size considerations

The expected relative proportions of diabetes type 2 patients developing microalbuminuria within the planned study period are: 24% in patients at high-risk for diabetic nephropathy in the treatment group receiving active study medication, 40% in those patients at high-risk for diabetic nephropathy in the placebo treated group and 8.5% in those therapy-naive patients at low-risk for diabetic nephropathy. Using the samples size formula for two proportions test ( $\alpha=0.05$   $\beta=0.80$ ), randomized (1:1),  $n=129$  in each arm of the intervention group. To account for an expected drop-out frequency of approx. 10% we plan to randomize 300 high-risk patients to double blind treatment with spironolactone treatment or matched placebo.

High-risk patients are expected to comprise 15% of the screened and included patients. In order to identify 300 high-risk patients the study requires 2000 patients to be included. To take screen failures of approx. 25% into account, we expect to screen 2700 patients.

Recruitment will continue until a minimum of 300 high risk patients are enrolled in order to preserve statistical power. Furthermore, at least 2000 patients in the overall study cohort will be included.

#### 15.1.1 Considerations of risk stratification

The study population will be stratified based on the CKD273 score at the screening visit. Patients with a CKD273 biomarker score above the level of 0.154 are classified as high-risk patients. The level of the cut-off is based on previous publications and unpublished data from >800 subjects with type 2 diabetes (20;22).

### 15.2 Study hypotheses

The null hypothesis of the study is that the probability for development of microalbuminuria is equal in both CKD273 pattern risk populations (low and high):

$$P(\text{microalbuminuria} \mid \text{high-risk population}) = P(\text{microalbuminuria} \mid \text{low-risk population}).$$

The alternative hypothesis is that the probability for microalbuminuria is lower in the low-risk population as judged by the CKD273 urinary proteomics pattern in comparison to patients in the high-risk population.

$$P(\text{microalbuminuria} \mid \text{high risk group}) > P(\text{microalbuminuria} \mid \text{low risk group}).$$

The significance level (type I error = probability of false rejection of the null hypothesis) for establishing the superiority of the CKD273 urinary proteomics pattern is 0.05 using a two-sided Cochran-Mantel Haenszel test.

### 15.3 Patient enrollment

Screening for eligible patients will be stopped, when at least 300 high-risk patients are enrolled in the interventions group and at least 2000 patients in the overall study.

## 15.4 Planned interim analyses

### 15.4.1 Safety review

The SAE and cases of death during IMP treatment in both arms of the intervention group will be reviewed by the Institute of Clinical Pharmacology of Hannover Medical School on an on-going basis. The Data Monitoring Committee will be provided with safety data to assess the overall safety of the study.

### 15.4.2 Efficacy review

No interim analysis for efficacy is planned.

## 15.5 Final analysis plan

Statistical analysis of the data will be performed by Steno Diabetes Center. A SAP will be written and signed before database lock and unblinding of the entire treatment code. Methods for imputation and type of censoring will be clarified in the SAP.

The primary efficacy analysis will be performed for all patients randomized, which is the intent-to-treat population. In addition, the primary and secondary efficacy endpoints will also be analyzed for the per-protocol population. The per-protocol analysis population includes all patients who were randomized into the double-blind study received study medication for at least 3 days.

For all analyses a p value <0.05 is considered significant.

Tables will be created for baseline variables, and comparisons performed between low- and high-risk population, and in the intervention group for active vs. placebo treatment. Furthermore, tables with observations from study visits will be provided for the observational part and for the intervention study.

Analyses not described here or in the SAP will be considered exploratory/post hoc analyses.

